- 15. Has or has had one or more of the following conditions considered clinically significant/relevant by the Investigator in the context of the study:
  - cardiovascular disease
  - congestive heart failure
  - cardiac hypertrophy
  - arrhythmia
  - bradycardia (pulse < 50 bpm)

  - tachycardia (pulse > 100 bpm)
  - respiratory disease
  - hepatic impairment or renal insufficiency
  - metabolic disorder
  - endocrine disorder
  - gastrointestinal disorder
  - hematological disorder
  - infectious disorder
  - any clinically significant immunological condition
  - dermatological disorder
- 16. Exhibits clinically significant abnormal vital signs at screening (see Note below).
- 17. Has one or more screening clinical laboratory test values outside the reference range that, in the opinion of the Investigator, are clinically significant, or any of the following (see Note below):
  - Serum creatinine > 1.5 × the upper limit of normal (ULN);
  - Serum total bilirubin > 1.5 × ULN;
  - Serum alanine aminotransferase or aspartate aminotransferase > 2 × ULN.
- 18. Has any of the following cardiology findings at screening (see Note below):
  - Abnormal ECG that is, in the Investigator's opinion, clinically significant;
  - PR interval > 220 ms;
  - QRS interval > 130 ms;
  - QTcF interval > 450 ms (for men) or > 470 ms (for women) (QT corrected using Fridericia's method);
  - Second- or third-degree atrioventricular block;
  - Any rhythm, other than sinus rhythm, that is interpreted by the Investigator to be clinically significant.

- 19. Has any disease or medication that could, in the Investigator's opinion, interfere with the assessments of safety, tolerability, or efficacy, or interfere with study conduct or interpretation of results.
- 20. Evidence of infection with hepatitis B or C, or human immunodeficiency virus (HIV)-1 or HIV-2, as determined by results of testing at screening.
- 21. Lost or donated more than 450 mL of blood during the 30 days prior to screening.
- 22. Use of any investigational drug or prohibited concomitant medications including known CYP1A2 substrates (e.g., theophylline, melatonin) within 30 days or 5 half-lives prior to Visit 1 (baseline) (whichever is longer) during the screening period or anticipated for the duration of the study.
- 23. History of unexplained loss of consciousness, unexplained syncope, unexplained irregular heartbeats or palpitations or near drowning with hospital admission.

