### 6.3.1. Adverse Events of Special Interest (AESI)

Adverse events of special interest (AESI) are defined as seizure or AEs that might represent a seizure. This includes, but is not limited to syncope/syncopal episode, pseudoseizure, myoclonus, and severe muscle spasms.

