4.5.1 Treatment-emergent Adverse Events

AEs will be coded using MedDRA Version 22.1. All AEs will be considered as treatmentemergent adverse events (TEAEs) and included in the AE summaries.

Adverse events will be categorized by MedDRA SOC and/or PT. A subject experiencing the same AE multiple times will only be counted once for that preferred term. Similarly, if a subject experiences multiple AEs within the same SOC, that subject will be counted only once for that SOC.

For displays, SOCs will be presented in alphabetical order and PTs will be sorted by decreasing incidence under each SOC.

An overview of TEAEs will be provided, this will include summaries of incidence rates (frequencies and percentages) of subjects who had at least one TEAE, serious TEAE, TEAE leading to death, TEAE by maximum severity, TEAE by relationship, TEAE leading to study drug discontinuation, related serious TEAE and Adverse Event of Special Interest (AESI).

TEAEs occurring in at least 5% of subjects will be presented by SOC and PT. TEAEs occurring in at least 5% of subjects by PT will also be presented. In addition, the incidence of TEAEs will also be summarized by MedDRA SOC, PT and maximum severity, in which subjects are counted once for each unique preferred term and each SOC under the known maximum severity at which it was experienced. If severity is unknown for all occurrences of a particular PT, it will be counted under 'severe'. The incidence of TEAEs by MedDRA SOC, PT and relationship to study drug will be produced in the same fashion.

AESIs include seizures or AEs that might represent a seizure (e.g., syncope/syncopal episode, pseudo seizure, myoclonus, severe muscle spasms). To identify the AESI, the following search terms will be used to search among the PTs as well as the verbatim terms: seizure, syncope, syncopal episode, pseudo seizure, myoclonus, and muscle spasms (that is categorized as severe only). The incidence of AESIs will be summarized by MedDRA SOC and PT. For subjects who experienced the same AESI multiple times, the event will be counted once.

4.5.2 Special Safety Categories: Death, Serious Adverse Events and Adverse Events Leading to Study Drug Discontinuation

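### The protocol defines its only adverse event of special interest openly, but the SAP finds it by six search terms alone, so the AESI outputs can undercount against that definition

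*SAP*

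**What the plan says.** Protocol 6.3.1 sets the concept: "Adverse events of special interest (AESI) are defined as seizure or AEs that might represent a seizure". It then marks its list as illustrative: "This includes, but is not limited to syncope/syncopal episode, pseudoseizure, myoclonus, and severe muscle spasms".

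SAP 4.5.1 restates the concept, also with examples: "AESIs include seizures or AEs that might represent a seizure (e.g., syncope/syncopal episode, pseudo seizure, myoclonus, severe muscle spasms". The next sentence gives the working rule. To identify AESIs, "the following search terms will be used to search among the PTs as well as the verbatim terms", and the terms are "seizure, syncope, syncopal episode, pseudo seizure, myoclonus, and muscle spasms (that is categorized as severe only". Nothing in that sentence marks the list as open.

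On reporting, the SAP states: "The incidence of AESIs will be summarized by MedDRA SOC and PT". Its lists of outputs assign this to Table 4.8, with a subject listing in Listing 4.5. The TEAE overview (Table 4.1) also counts subjects with an AESI.

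**The concern.** The examples that illustrate the definition have become the whole identification rule. An event a clinician would accept as possibly a seizure, but which is worded or coded without one of the six strings, would not reach the AESI outputs.

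Long-term safety is the primary objective (Protocol 2.1), AEs are among the primary endpoints (Protocol 2.3), and possible seizure is the only event class singled out. A reader of Table 4.8 will take it as the count of AESIs as the protocol defines them. If the search is narrower than the definition, the table can read as complete when it is not. Few events would be expected, so each unlabelled one matters to the result.

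The rule also cannot be programmed in only one way, because the SAP does not say whether a term must match exactly or may be part of a longer string.

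**Working it through.** The documents give no AESI rate, event count or power calculation (Protocol 7.10 states that none was considered), so there is no planned figure to reproduce. The check is mainly a comparison of texts.

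**1. Definition against rule.** Protocol 6.3.1 is open ("This includes, but is not limited to"). The opening sentence on AESIs in SAP 4.5.1 is open too, since it uses e.g. The search list is closed at six terms: the protocol's examples plus seizure itself.

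**2. Other routes into the AESI set.** Protocol 6.3.3 lists what the investigator determines for each AE: seriousness, causality and severity. AESI status is not among them. Protocol 6.3.8, on other events for immediate reporting, does not mention AESIs. The SAP text gives no MedDRA grouping and no medical review of terms.

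**3. What the six strings catch.** Each phrase was compared with the six terms, ignoring case. Phrases marked † are illustrative and are not taken from the documents.

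| Phrase | Substring match | Exact match |
|---|---|---|
| seizure; syncope; syncopal episode; myoclonus | yes | yes |
| pseudoseizure (protocol spelling) | yes, through *seizure* | no |
| seizure disorder; seizure-like events | yes | no |
| loss of consciousness | no | no |
| convulsion†; epilepsy†; blackout†; fainting† | no | no |
| myoclonic jerk† | no | no |
| muscle spasm† (singular) | no | no |

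Exclusion B23 of the protocol reads "History of unexplained loss of consciousness, unexplained syncope, unexplained irregular heartbeats or palpitations", so the protocol's own vocabulary words loss of consciousness separately from syncope. Under exact matching the rule would also fail on the protocol's one-word spelling of pseudoseizure. Under substring matching, a separate entry for the two-word form is redundant beside *seizure*.

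**4. Where an unmatched event would appear.** By its title, Table 4.2 shows all TEAEs by system organ class and PT, and Listing 4.1 holds all AEs. The event would be there without the AESI label. It would enter the table of events in at least 5% of subjects only if enough subjects had that PT: 0.05 × 366 = 18.3, so 19 subjects at maximum enrolment.

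**5. Scale, as illustration only.** The input from the documents is N = 366, the enrolment maximum. The event counts, rates and sensitivities are assumptions.

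Exact (Clopper-Pearson) two-sided 95% intervals:
- 0/366: the upper limit is 1 − 0.025^(1/366) = 1.00%.
- 1/366 = 0.27%: the limits are the 0.025 quantile of Beta(1, 366) and the 0.975 quantile of Beta(2, 365), which gives 0.01% to 1.51%.
- 2/366 = 0.55%: 0.07% to 1.96%.

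One-sided 95% upper limits are lower: about 3.0/366 = 0.8%, 4.74/366 = 1.3% and 6.30/366 = 1.7% for 0, 1 and 2 subjects.

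The chance that at least one AESI is labelled is 1 − (1 − p·s)^366, for true subject rate p and search sensitivity s:

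| p | s = 1 | s = 0.75 | s = 0.5 |
|---|---|---|---|
| 0.25% | 0.60 | 0.50 | 0.37 |
| 0.5% | 0.84 | 0.75 | 0.60 |
| 1% | 0.975 | 0.94 | 0.84 |

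**The case against.** The strongest reply is that a pre-specified, printed term list is a legitimate and reproducible way to make an open concept operational. Protocol 7.1 lets the SAP supersede the protocol's statistical methods, and anyone can see what Table 4.8 contains. That has force as an argument for keeping the list. It does not close the gap, because the SAP itself repeats the open concept in the sentence before the list and does not say that it means to narrow it.

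Several further points stand and limit the finding:

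- **Coding may recover variants.** PTs are searched as well as verbatim terms, and SAP 2.6.1 assigns lower level terms to PTs. A verbatim *myoclonic* is lost only if its PT also lacks every string. The documents do not give the coding.
- **Recognised seizures have another route.** Protocol 6.3.6 gives a seizure without hospital admission as an event that would typically be considered serious. Such events would normally also reach Table 4.6 and Listing 4.2.
- **B23 is limited evidence.** It is an entry criterion for Schedule B only, and it sits beside palpitations and near drowning. It shows separate wording; it does not show that the protocol regards loss of consciousness as a possible seizure. That reading rests on the open phrase in 6.3.1.
- **The list can also over-include.** Syncope and severe muscle spasms count whatever their cause, and a substring search would pick up *presyncope*.
- **Not everything was available.** The eCRF and the table shells (SAP Appendix B) were not seen. The absence of an AESI flag or a review is a statement about the protocol and SAP text only.

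**Conclusion.** The point holds: the identification rule in SAP 4.5.1 is narrower than the definition it implements, its matching is unspecified, and neither document describes another route. Relative to the protocol definition, events left out can only lower the count in Table 4.8, Listing 4.5 and the AESI row of the overview. The number of events affected cannot be stated from the documents. The intervals and probabilities above show only that single events matter at this sample size. The SAP plans no confidence interval for AESIs, and nothing supports a particular miss rate. The change is worth making, but the general AE reporting does not depend on it.

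A reader might infer more, and the documents do not support it:

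- **That possible seizures would vanish from the report.** They would lose the AESI label but stay in the general AE table and listing.
- **That the AESI count is biased downward in every sense.** This is true only against the protocol definition. As a count of actual seizures, the list can err upward as well.
- **That seizure history is excluded because seizure is the AESI.** Exclusion A3 gives no reason, and B5 refers to effects on central nervous system functioning.

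**What to change.** Revise the AESI paragraph in SAP 4.5.1 to:

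1. Keep the six terms as a first pass.
2. State that matching ignores case and uses substrings or stems, covering singular and plural forms, one- and two-word spellings, and adjectival forms such as *myoclonic*.
3. Add terms for loss of consciousness, convulsion and epilepsy, or name a pre-specified MedDRA grouping that covers them.
4. Require a documented medical review of all AE PTs and verbatim terms against Protocol 6.3.1 before database lock, with the selected events added to Table 4.8, Listing 4.5 and the AESI row of Table 4.1.

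This costs one SAP paragraph and one short review, with no new data collection. An investigator AESI flag would be optional. The downside is a few non-specific events in the AESI table, which the protocol's wide definition already accepts. Identifying in Listing 4.5 whether each event came from the search or the review would let readers separate the two.

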### 7.9. Safety Analysis

Safety analyses will be performed by optimized dose group and overall based on the Safety Population.

The incidence rate of AEs will be calculated for each system organ class (SOC) and preferred term (PT). The severity of the AEs and the relationship to SM will be summarized for each SOC and PT.

AEs will be summarized using discrete summaries at the subject and event level by SOC and PT, and by severity and relationship separately. Verbatim description and Medical Dictionary for Regulatory Activities (MedDRA) SOCs and PTs for all AEs will be contained in the subject data listings.

Clinical laboratory values will be summarized by visit by optimized dose group and overall using descriptive statistics. For quantitative laboratory parameters, both actual values and change from baseline values will be summarized.

Vital signs will be summarized by visit by optimized dose group and overall using descriptive statistics. Both actual values and change from baseline will be summarized.

ECG results will be summarized by visit by optimized dose group and overall using descriptive statistics (for quantitative ECG parameters) and frequency tables (for qualitative ECG parameters, including the overall ECG finding).

C-SSRS outcomes will be summarized using number and percent of subjects by categories for suicidal ideation only, suicidal behavior only and suicidality (ideation and behavior combined). The summary will be presented by optimized dose group and overall.

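### Protocol 7.9 plans AE summaries by subject and by event; SAP 4.5.1 describes only once-per-subject counts and does not say that the event level was dropped

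*SAP*

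**What the plan says.** Protocol 7.9 names two units of count: "AEs will be summarized using discrete summaries at the subject and event level by SOC and PT, and by severity and relationship separately". AEs are among the primary safety endpoints (Protocol 2.3).

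The counting rules in SAP 4.5.1 are these:

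- Preferred term: "A subject experiencing the same AE multiple times will only be counted once for that preferred term".
- SOC: "if a subject experiences multiple AEs within the same SOC, that subject will be counted only once for that SOC".
- Overview table: "summaries of incidence rates (frequencies and percentages) of subjects who had at least one TEAE", and likewise for its other categories.
- Severity: "subjects are counted once for each unique preferred term and each SOC under the known maximum severity at which it was experienced".
- Relationship: "The incidence of TEAEs by MedDRA SOC, PT and relationship to study drug will be produced in the same fashion".
- AESI: "For subjects who experienced the same AESI multiple times, the event will be counted once".

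SAP 4.5.2.2 and 4.5.2.3 present SAEs and AEs leading to discontinuation as incidences by SOC and PT. In SAP 5.1, none of Tables 4.1 to 4.8 is titled as a count or rate of events. SAP 5.2 plans listings of all AEs (4.1), SAEs (4.2), AEs leading to discontinuation (4.4) and AESIs (4.5).

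Two other provisions bear on the point. Protocol 7.1 gives the SAP precedence over the protocol's statistical methods. SAP 5 refers to Appendix B for the table shells, which are not among the documents available for this review.

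**The concern.** The primary objective is long-term safety, and recurrence is one of the things that long follow-up can show. Counting a subject once per term answers how many people had the event. It does not answer how often the event came back. The protocol planned for both questions, and the SAP as described answers the first.

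The AESI sentence is the sharpest instance. AESIs are seizures and events that could be seizures (Protocol 6.3.1). The sentence goes a step beyond the usual incidence convention: read literally, it collapses the episodes and not just the subject. It also leaves open whether the same AESI means the same preferred term or the same category. Within one preferred term, a subject with a single episode and a subject with several add the same amount to Table 4.8.

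At stake is whether a reader of the safety tables can tell isolated events from recurring ones without counting lines in the listings.

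**Working it through.** The documents state no event count or rate, so there is no figure to reproduce. The check is a comparison of texts, followed by an illustration of size.

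**Step 1. Unit of count, side by side.**

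| Summary | Protocol 7.9 | SAP 4.5.1 and 4.5.2 |
|---|---|---|
| By SOC and PT | subjects and events | subjects, once per PT and once per SOC |
| By severity | subjects and events | subjects, once at maximum severity |
| By relationship | subjects and events | subjects, same rule as severity |
| SAEs, discontinuations | not separated from other AEs | incidence by SOC and PT |
| AESIs | not separated from other AEs | incidence by SOC and PT, repeats counted once |

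The event level is missing from every row on the SAP side, and the SAP text gives no reason.

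**Step 2. Opportunity to record a repeat.** Protocol Tables 1 and 2 schedule Visits 2 to 22 (21 visits), 19 interim calls (Days 57 to 1065) and a final safety call (Day 1100): 21 + 19 + 1 = 41 contacts after the first dose. Unscheduled visits, and the 8-weekly visits that may follow Visit 22, can add to this.

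**Step 3. How much a once-per-subject table can miss.** Inputs from the documents: N = 366 subjects at most, and T = 156 weeks. Assumptions: all 366 are followed for the full period, and events of one PT occur independently at a constant rate r per subject-year (Poisson). The values of r are assumed, to show a range.

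- T = 156 × 7 / 365.25 = 2.990 years; N × T = 1,094 subject-years at most.
- Expected events: E = N × r × T.
- Expected subjects counted: S = N × (1 − exp(−r × T)).
- Share of events not tabulated: 1 − S/E.

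| r per subject-year | E | S | Not tabulated |
|---|---|---|---|
| 0.02 | 21.9 | 21.2 | 3% |
| 0.1 | 109.4 | 94.6 | 14% |
| 0.5 | 547.1 | 283.9 | 48% |
| 1.0 | 1,094.2 | 347.6 | 68% |

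Example for r = 0.5: E = 366 × 0.5 × 2.990 = 547.1; S = 366 × (1 − exp(−1.495)) = 283.9; 1 − 283.9/547.1 = 48%.

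Early dropout lowers these shares. Clustering of events within subjects raises them.

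**The case against.** The case on the other side is substantial, and much of it stands.

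- **Precedence.** A reader might infer that the SAP breaches the protocol. It does not: Protocol 7.1 lets the SAP prevail. What remains is a change to a planned summary of a primary safety endpoint that the SAP neither announces nor explains.
- **Listings.** A reader might infer that information on recurrence is lost. It is not: repeats should appear in Listings 4.1, 4.2, 4.4 and 4.5, and with few AESIs, Listing 4.5 would be short enough to read episode by episode. The gap is one of tabulation. Even so, Protocol 7.9 asks for event-level summaries and treats listings as a separate item.
- **Other tables separate cases too.** Seriousness (Table 4.6), discontinuation (4.7) and maximum severity (4.4) distinguish some troublesome events from mild ones, and different AESI terms in one subject are still counted separately by PT. None of these shows frequency.
- **Unseen shells.** Appendix B could contain an event column, so it cannot be said for certain that no table will have one. Nothing in the SAP text or table titles points to one, and in Table 4.8 it would conflict with the AESI sentence.
- **Comparison with 812P306.** It is tempting to argue that the parent trial was too short to show recurrence. Neither document gives its treatment duration, so that argument is not available.
- **Reliability of event counts.** Protocol 6.3.4 grades severity over the period since AEs were last recorded, so one continuing event could be entered in several records. Raw counts under variable follow-up are also hard to read. Both objections are sound; they call for a merge rule and a person-time denominator.

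**Conclusion.** The mismatch between Protocol 7.9 and SAP 4.5.1 is plain on the text. As the SAP is described, the AE tables report who had an event and not how many events there were, and the change is not acknowledged. This is a shortfall in summary tables, to be corrected or justified.

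Its size cannot be fixed from the documents. In the illustration it is small for rare terms (about 3% of events at 0.02 per subject-year) and large for common recurring ones (about 48% at 0.5). Those figures rest on assumed rates, independent events and full follow-up of 366 subjects. For seizure-like AESIs, if they are rare, the numerical loss would be small unless episodes cluster in a few subjects. The conclusion also assumes that the unseen shells follow the SAP text.

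**What to change.** In SAP 4.5.1:

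1. Keep n (%) of subjects and add the number of events, E, to Tables 4.1, 4.2 and 4.6 to 4.8, preferably with events per subject-year. The exposure duration defined in SAP 4.3 can supply the denominator.
2. For severity and relationship, tabulate events by each event's own grade or relationship, separately from the subject counts in Tables 4.4 and 4.5. A maximum-severity layout cannot take an event column directly.
3. Replace the AESI sentence with: *subjects are counted once per PT; all episodes are counted as events.*
4. Add a merge rule: *consecutive records of one continuing event (same PT, no resolution between them) count as one event.* State which grade and relationship a merged event takes.

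If the sponsor prefers subject counts only, the SAP should say that the event level in Protocol 7.9 was dropped, and why.

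The cost is modest. No new data are needed, because Protocol 6.3.3 already has all AEs after the first dose recorded. There is an added column in five tables, an event tabulation for severity and for relationship, and the merge step. The remaining weakness is that event counts still depend partly on how sites split continuing events.

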4.5.2.1 Deaths

A listing of deaths will be presented.

